## 9.0 STATISTICAL CONSIDERATIONS

### 9.1 Sample Size and Study Duration

#### 9.1.1 Non-osteosarcoma strata

Three disease strata have been identified for reporting upon completion of evaluation of each particular disease stratum (“primary disease groups”). These strata are: (1) Ewing sarcoma; (2) rhabdomyosarcoma; and (3) non-rhabdomyosarcoma soft tissue sarcoma. The evaluation rule is described in [Section 9.2](#) below.

In addition to the three main strata, enrollment into each of the following tumor groups (“secondary strata”): (4) Wilms tumor, and (5) rare tumors (medullary thyroid carcinoma, renal cell carcinoma, hepatocellular carcinoma, hepatoblastoma, adrenocortical carcinoma, and pediatric solid tumors with known molecular alterations in the targets of XL184); will be open to accrual. If thirteen response-evaluable patients of a particular histology are enrolled in any of the secondary strata, the two-stage design described in [Section 9.2](#) below will be applied to that particular histology. (That is, up to seven additional response-evaluable patients with that tumor type may be studied.)

If two of the three primary disease strata (Ewing sarcoma, rhabdomyosarcoma, and non-rhabdomyosarcoma STS) have met their accrual and one remains open, the Cancer Therapy Evaluation Program (CTEP) and the ADVL1622 Investigators will discuss the study timeline.

Review of patient accrual onto recent phase 2 solid tumor studies indicates the following entry rates for the various tumors under study can be expected:

Disease Group/Strata	Patients/Year
Ewing sarcoma	18
Rhabdomyosarcoma	18
Non-rhabdomyosarcoma STS	10

With these entry rates, the probability of accruing 13 patients to complete the initial stage of evaluation in the three primary disease groups within 19 months is 80% and within 24 months is 90%. The corresponding probability for enrolling 20 patients in the three named disease categories within 28 months is 80% and within 37.5 months is 90%. The study will likely require 2 to 3 years for sufficient patient enrollments to evaluate response in the primary disease groups. If activity is detected in any category, further trials in subcategories of category may be conducted at the discretion of the Developmental Therapeutics Steering and study committees. If all three statistical cohorts are finished accruing (either all 20 patients or 13 patients with the early stopping criterion met), the Study Committee will evaluate the non-statistical strata and make a decision whether to continue accrual to those strata. A minimum of 39 patients and a maximum of 110 patients are anticipated to get either 13 or 20 patients evaluable for response in each statistical stratum.

#### 9.1.2 Osteosarcoma Cohort

Review of patient accrual onto recent phase 2 solid tumor studies indicates the following entry rates for the osteosarcoma stratum can be expected:

Disease Group/Strata	Patients/Year
Osteosarcoma	22

With this entry rate, the probability of accruing 19 patients to complete the initial stage of evaluation in the osteosarcoma stratum within 12.3 months is 80% and within 18.2 months is 90%. The corresponding probability for enrolling 29 patients in the osteosarcoma stratum within 20 months is 80% and within 26 months is 90%. The osteosarcoma will likely require 1.5 to 2.5 years for sufficient patient enrollments to evaluate response in osteosarcoma. A minimum of 19 patients and a maximum of 36 patients are anticipated to get either 19 or 29 patients evaluable for response in the osteosarcoma stratum.

When the evaluation of the statistical strata (Ewing’s sarcoma, rhabdomyosarcoma, non-rhabdomyosarcoma STS, and osteosarcoma) is complete, enrollment to the study will be terminated. The non-statistical cohorts will remain open to enrollment until the statistical strata are closed to accrual unless the DVL committee leadership indicates further enrollment on the secondary strata is warranted.

## 9.2 Study Design

### 9.2.1 Non-osteosarcoma Strata

The primary endpoint for the non-osteosarcoma strata will be objective response by RECIST criteria v 1.1. The best response of disease to XL184 (defined in [Section 10.4](#)) will be examined separately in each of the 3 primary disease groups. If 13 patients of the same histology enroll on either of the secondary strata (i.e., 13 Wilms tumor patients or 13 of the same type of eligible rare tumor patients), then the rule below will be applied to that group of patients. The following Simon’s minimax two-stage design will be used in all the non-osteosarcoma strata.

	Cumulative Number of Responses	Decision
Stage 1: Enter 13 patients	0	Terminate the trial early: agent ineffective
	1 or more	Inconclusive result, continue trial (proceed to Stage 2)
Stage 2: Enter 7 additional patients	2 or fewer	Terminate the trial: agent ineffective
	3 or more	Terminate the trial: agent effective

We will consider the agent not of sufficient interest for further evaluation in a disease category if the true response rate is 5% and of sufficient activity if the true response rate is 25%. If the agent has a true response rate of 5%, the rule described above will identify it of sufficient activity for further study with probability 0.074 (type I error),

and the trial will have an expected sample size of 16.4 with 51.3% probability of early termination. If the agent has a true response rate of 25%, the rule described above will identify it of sufficient activity for further study with probability 0.903 (power against the alternative hypothesis  $p = 0.25$ ). An expanded table of possibilities is below:

True response rate	Probability of stopping early for lack of activity	Probability of identifying agent as effective	Expected number of patients accrued
5%	0.513	0.074	16.41
10%	0.254	0.317	18.22
15%	0.121	0.586	19.15
20%	0.055	0.786	19.62
25%	0.024	0.903	19.83
30%	0.010	0.961	19.93
35%	0.004	0.986	19.97

### 9.2.2 Osteosarcoma stratum-specific Design

For the osteosarcoma stratum, patients will be enrolled in two stages. In the first stage, 19 disease control and RECIST response evaluable patients will be enrolled. Each patient will be evaluated for both outcome measures: (1) disease control success; and (2) RECIST response (CR or PR v. not CR or PR). The decision rule for the two stage study design is summarized as:

	Cumulative response results	Decision
Stage 1: Enter 19 patients	$\leq 4$ disease control successes AND $\leq 1$ RECIST responders	Terminate the trial early: agent ineffective
	$\geq 5$ disease control successes OR $\geq 2$ RECIST responders	Inconclusive result, continue trial (proceed to Stage 2)
Stage 2: Enter 10 additional patients	$\leq 8$ disease control successes AND $\leq 4$ RECIST responders	Terminate the trial: agent ineffective
	$\geq 9$ disease control successes OR $\geq 5$ RECIST responders	Terminate the trial: agent effective

*Design Characteristics:* Each patient enrolled will be evaluated for: (1) complete or partial response as defined by the RECIST criteria where the first evaluation of CR or PR is made at or before the end of the sixth cycle of study therapy (denoted as R below); or (2) stable disease after four months of therapy or at the end of the sixth cycle, whichever occurs first (denoted as S below). We will not be interested in promoting the agent for further investigation if the probability of response in any particular individual is less than or equal to 0.05 ( $P(R) \leq 0.05$ ) and the probability of remaining analytic event free in any particular individual is less than or equal to 0.20 ( $P(S) \leq 0.20$ ). We will be interested in promoting the agent for further investigation if the probability of response in any particular individual is

at least 0.22 ( $P(R) \geq 0.22$ ) **or** the probability of remaining analytic event free in any particular individual is at least 0.42 ( $P(S) \geq 0.42$ ).

For the calculations below, it is assumed  $\Pr(S | R) = 0.90$ .

The statistical characteristics of this design are:

Probability of four month disease control	Probability of RECIST response	Probability of Stopping After Stage 1 (and concluding the drug is ineffective)	Probability of Concluding the Drug is Ineffective at the Conclusion of the Trial	Probability of Concluding the Drug is Effective at the Conclusion of the Trial
0.20	0.05	0.56	0.89	0.11
0.42	0.22	0.014	0.05	0.95
0.42	0.05	0.044	0.096	0.904
0.20	0.22	0.056	0.21	0.79

### 9.3 Methods of Analysis

Toxicity tables will be constructed to summarize the observed incidence by type of toxicity and grade. A patient will be counted only once for a given toxicity for the worst grade of that toxicity reported for that patient. Toxicity information recorded will include the type, severity, time of onset, time of resolution, and the probable association with the study regimen.

Time-to-event analyses (time to progression, progression-free survival, and overall survival) will be computed when all patients in a stratum have at least one year of follow-up.

#### 9.3.1 RECIST Response Criteria for all strata

Response criteria are described in [Section 10](#). A RECIST responder is defined as a patient who achieves a best response (as defined in [Section 10.6](#)) of PR or CR on the study. Response rates will be calculated as the percent of RECIST response-evaluable patients who are responders, and confidence intervals will be constructed accounting for the two-stage design.

#### 9.3.2 Disease control for osteosarcoma stratum

Any patient who is evaluated free of all detectable disease (complete response) or is considered as having a partial response or is considered as having stable disease ('at least stable disease') after four months of therapy or at the end of the sixth cycle, whichever occurs first, will be considered a disease control success.

Any evaluable patient who does not meet the criteria for disease control success (complete response, partial response or stable disease) will be considered to not have experienced disease control success.

In particular, any patient who dies because of treatment-related toxicity during the first six cycles of therapy and/or within the first four months since starting treatment will be considered not to have experienced disease control success. Also, any patient who is eligible, receives one dose of XL184 and is lost to follow-up at (for example) the end of cycle 2 will not be considered a disease control success (complete response, partial response or stable disease)

Patients who are not evaluable for both disease control and response evaluation may be replaced for the purposes of the statistical rule.

9.3.3 Osteosarcoma Estimation of Disease Control and RECIST Response Rates

P(R) and P(S) for the osteosarcoma cohort will be estimated using the maximum likelihood estimates, viz.

$$P(R) \hat{=} \hat{p}_R = \frac{\text{Number of Patients Considered as PR or CR}}{\text{Number of Response-Evaluable Patients in Cohort}}$$

$$P(S) \hat{=} \hat{p}_S = \frac{\text{Number of Patients with Disease Control at 4 Months}}{\text{Number of Response-Evaluable Patients in Cohort}}$$

Confidence intervals will be constructed using the approximate normal distribution of each of the estimates and their asymptotic variances:

$$V(\hat{p}_R) \hat{=} \frac{\hat{p}_R(1 - \hat{p}_R)}{\text{Number of Response-Evaluable Patients in Cohort}}$$

$$V(\hat{p}_S) \hat{=} \frac{\hat{p}_S(1 - \hat{p}_S)}{\text{Number of Response-Evaluable Patients in Cohort}}$$

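### Section 9.3.3 prescribes Wald intervals for the osteosarcoma rates at 19 or 29 patients; at the design null the response-rate interval covers about 65%, and for that rate it also conflicts with Section 9.3.1

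*Combined protocol and SAP*

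**What the plan says.** Section 9.3.3 estimates P(R), the RECIST response rate, and P(S), the four-month disease control rate, by simple proportions of response-evaluable patients. It then says "Confidence intervals will be constructed using the approximate normal distribution of each of the estimates and their asymptotic variances". The variances it prints are p(1-p)/n for each rate, with no term for the stage reached. No confidence level appears in 9.3.1 or 9.3.3.

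Section 9.3.1 is headed "RECIST Response Criteria for all strata" and says of response rates that "confidence intervals will be constructed accounting for the two-stage design". It does not mention disease control.

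The sample size comes from Section 9.2.2: "In the first stage, 19 disease control and RECIST response evaluable patients will be enrolled", followed by "Stage 2: Enter 10 additional patients" if the first stage does not stop. The trial stops after stage 1 with at most 4 disease control successes and at most 1 responder. After 29 patients it declares activity with at least 9 successes or at least 5 responders. The null is P(R) = 0.05 and P(S) = 0.20, and the plan's calculations assume Pr(S|R) = 0.90.

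**The concern.** The normal approximation needs a reasonable expected number of events. Here the expected number of responders at the null is 19 × 0.05 = 0.95 at stage 1 and 29 × 0.05 = 1.45 at the full sample. With no responders the estimated variance is zero and the interval collapses to a point at 0%. With very few responders the lower limit falls below zero.

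The stopping rule makes this worse. An early stop requires 0 or 1 responder, so every trial that stops early would report either 0% to 0% or, for 1/19 at the 95% level, -4.8% to 15.3%. The formula fails in the very outcome that the interim look is meant to detect.

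P(R) also falls under two instructions that cannot both be followed, because the 9.3.3 formula ignores the stages and 9.3.1 requires that they be taken into account. For P(S), 9.3.3 is the only instruction, so the method is weak but not contradicted.

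These are the estimates for the stratum's primary aim (Section 1.1.2). A reader who sees a response rate of 0% with no uncertainty would take the data to be far more conclusive than 19 patients can be.

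**Working it through.** **Inputs.** Stage sizes 19 and 10, the decision rule, the null and target rates and Pr(S|R) = 0.90, all from Section 9.2.2; variance p(1-p)/n from Section 9.3.3. Assumption: two-sided 95% intervals (z = 1.96), with 90% and 99% as a range.

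**Step 1: reproduce the plan's table.** At the null, each patient falls in one of four cells:

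- response and disease control: 0.90 × 0.05 = 0.045
- response only: 0.05 - 0.045 = 0.005
- disease control only: 0.20 - 0.045 = 0.155
- neither: 0.795

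Exact multinomial enumeration over 19 and then 10 more patients gives:

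| P(S), P(R) | Stop at stage 1: plan / recomputed | Effective: plan / recomputed |
|---|---|---|
| 0.20, 0.05 | 0.56 / 0.564 | 0.11 / 0.108 |
| 0.42, 0.22 | 0.014 / 0.0135 | 0.95 / 0.949 |
| 0.42, 0.05 | 0.044 / 0.045 | 0.904 / 0.904 |
| 0.20, 0.22 | 0.056 / 0.057 | 0.79 / 0.789 |

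The model is therefore the plan's own.

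**Step 2: probability of a 0% to 0% interval at the null.** No responders in 19 has probability 0.95^19 = 0.377. Adding the condition of at most 4 disease control successes, the trial stops there with probability 0.307. The remaining 0.377 - 0.307 = 0.070 continues, and has no responder among the next 10 with probability 0.95^10 = 0.599, giving 0.070 × 0.599 = 0.042. The total is 0.307 + 0.042 = 0.349.

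**Step 3: coverage of p ± 1.96 √(p(1-p)/n) at the final n, under the two-stage rule.**

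| P(S), P(R) | Wald, P(R) | Wald, P(S) |
|---|---|---|
| 0.20, 0.05 | 64.8% | 89.7% |
| 0.42, 0.05 | 76.0% | 91.5% |
| 0.20, 0.22 | 87.4% | 89.8% |
| 0.42, 0.22 | 88.9% | 93.3% |

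At P(R) = 0.10, Wald coverage of P(R) is 86.5% with P(S) = 0.20 and 93.6% with P(S) = 0.42.

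At the null, non-coverage of P(R) is 35.2 points: 34.9 from zero responders and 0.3 from six or more responders out of 29, where the lower limit exceeds 5%. A further 59.9% of outcomes (1/19, or 1 to 3 out of 29) have a negative lower limit, although those intervals do contain 5%.

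**Step 4: is the interim look the cause?** No. Under the same two-stage rule at the null, with no stage adjustment, Wilson covers P(R) 94.9% and Clopper-Pearson 98.7%. The failure lies in the Wald formula.

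**Step 5: sensitivity at the null.** Wald coverage of P(R) is 63.8% at a 90% level and 65.1% at a 99% level. At 95% it is 66.0% with Pr(S|R) = 0.5 and 64.6% with Pr(S|R) = 1.0.

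**Reachable results at 95%.**

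| Responders | Wald | Clopper-Pearson |
|---|---|---|
| 0/19 | 0 to 0% | 0 to 17.6% |
| 1/19 | -4.8 to 15.3% | 0.1 to 26.0% |
| 0/29 | 0 to 0% | 0 to 11.9% |
| 1/29 | -3.2 to 10.1% | 0.1 to 17.8% |

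**The case against.** The strongest reply is that nothing decisive depends on these intervals. The stopping and final rules use counts, the intervals can be recomputed from published counts, and a 0% to 0% interval is so plainly degenerate that few readers would be misled. Away from zero responders, the shortfalls for P(S), and for P(R) at 0.22, are ordinary small-sample Wald behaviour. Section 9.3.3 is also the more specific text, so it can be read as governing osteosarcoma, which would leave no real conflict with 9.3.1.

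The point about decisions stands and limits the seriousness of the problem. The rest stands only in part. The plan fixes a method that fails for about one null trial in three, and replacing it after the data are seen is what prespecification is meant to avoid. The specific-over-general reading is reasonable, but 9.3.1 says it covers every stratum and nothing in the text gives 9.3.3 precedence.

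Two further arguments against Wald deserve little weight. Negative lower limits could simply be cut at zero without affecting coverage, and some depend on the level: 3/29 has a lower limit of -0.7% at 95% but +1.0% at 90%. Nor does disagreement with the decision thresholds prove much. At 5/29 the 95% Wald interval (3.5 to 31.0%) includes the 5% null and the exact one (5.8 to 35.8%) does not, but at 90% Wald (5.7 to 28.8%) excludes it too. At 9/29 disease control successes, all three 95% intervals include the 20% null.

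**Conclusion.** The concern holds. The method in 9.3.3 gives wrong error bars for a primary estimate. At the design null, a nominal 95% interval for P(R) covers 64.8%, and there is a 34.9% chance of reporting 0% with no uncertainty. Coverage of P(R) is 76.0 to 88.9% at the other three design points. For P(S) the shortfall is modest. The mismatch between 9.3.1 and 9.3.3 concerns P(R) only.

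The figures assume a 95% level, the 19/29 rule followed as written and Pr(S|R) = 0.90; the null result barely moves when the level or Pr(S|R) is varied. Stopping, type I error and power are unaffected. It should be fixed, but it does not threaten the design.

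**What to change.** In 9.3.3, delete the normal-approximation sentence and both variance formulas, and put in their place: *Two-sided 95% Clopper-Pearson intervals will be reported for P(R) and P(S), using the number of evaluable patients at the stage reached.* Wilson is an acceptable alternative. At the four design points, under the two-stage rule and across both rates, Clopper-Pearson covers 95.9 to 98.7% and Wilson 93.3 to 96.6%. Clopper-Pearson is the conservative choice, and Wilson is closer to nominal for P(R).

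Neither interval formally adjusts for the two stages, so 9.3.1 should be reworded too: stage-adjusted intervals apply to the non-osteosarcoma strata, and osteosarcoma uses the 9.3.3 interval because its stopping rule depends on both outcomes. This gives up a formal adjustment for osteosarcoma, which the coverage figures above support. If the sponsor prefers a two-stage exact interval there, the plan must state how outcomes are ordered and how P(S) and Pr(S|R) are handled when inferring P(R); at present it states neither.

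The cost is one sentence in each section and, in the low-count results that matter most, wider reported intervals. Enrolment, data collection and the decision rule do not change. A two-stage exact interval would need extra specification and programming.

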9.3.4 Adverse Event Monitoring Rule

We will use a Bayesian rule to monitor for protocol-specific toxicities. We will assume a beta prior distribution with  $\alpha = 0.52$  and  $\beta = 2.08$ . At least once per month, we will calculate the posterior probability (given the data) that the probability of protocol-specific toxicity exceeds the 20% threshold:

$$P(p_{\text{protocol-specific toxicities}} > 20\% | \text{Data}) = \int_{0.2}^1 \frac{\binom{n}{x} p^x (1-p)^{n-x} \frac{\Gamma(2.6)}{\Gamma(0.52)\Gamma(2.08)} p^{-0.48} (1-p)^{1.08}}{\int_0^1 \binom{n}{x} q^x (1-q)^{n-x} \frac{\Gamma(2.6)}{\Gamma(0.52)\Gamma(2.08)} q^{-0.48} (1-q)^{1.08} dq} dp$$

Here  $n$  is the number of protocol-specific toxicity-evaluable cycles and  $x$  is the number of such cycles on which a protocol-specific toxicity event is observed. Examples of situations in which this rule will indicate protocol-specific toxicities have been noted and are presented below:

Number of failures	Number of patient-cycles
2	6
3	10
4	14
5	19
6	23
7	28
8	32
9	37
10	41
11	46
12	51

13	55
14	60

Protocol-specific toxicities of interest include fatigue, headache, proteinuria, hypertension, reversible posterior leukoencephalopathy syndrome (RPLS), palmar-plantar erythrodysesthesia, oral mucositis, ALT increase, lipase increase, bilirubin increase, diarrhea, thrombocytopenia, hypothyroidism, nausea, anorexia, neutropenia, weight loss and vomiting.

If there is strong evidence (posterior probability of at least 70% with at least 2 observed toxicities) that there is a per course protocol-specific toxicity probability of more than 20%, such information will be presented to the DSMC.

#### 9.4 Evaluability for Response

Any patient who is enrolled and receives at least one dose of XL184 will be considered evaluable for response and disease control provided: (1) the patient demonstrates progressive disease or death while on protocol therapy; or (2) the patient is observed on protocol therapy for at least one cycle and the tumor is not removed surgically prior to the time complete response or partial response is confirmed, or (3) the patient demonstrates a complete or partial response as confirmed according to protocol criteria. Patients who demonstrate a complete or partial response confirmed by central review will be considered to have experienced a response for the application of the rule given in [Section 10.2](#). The evaluation period for determination of the best response will be 6 treatment cycles. All other patients will be considered non-responders. All patients considered to have a response (CR or PR) must have imaging studies reviewed centrally at the COG. Centers will be notified by the COG about requests for scans of patients with stable disease. See [Section 7.3](#) regarding shipping instructions. Preliminary assessment of activity using institutionally provided tumor measurements will be entered into CDUS quarterly. The central review by COG will be provided as the final reviewed assessment of response when such becomes available.

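### Section 9.4, read literally, leaves treated patients who stop in Cycle 1 without progression or death out of both efficacy denominators, and no all-treated analysis shows the effect

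*Combined protocol and SAP*

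**What the plan says.** Section 9.4 gives three routes by which a dosed patient becomes evaluable for response and disease control:

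- "the patient demonstrates progressive disease or death while on protocol therapy";
- "the patient is observed on protocol therapy for at least one cycle", provided the tumor is not resected before a response is confirmed;
- a confirmed complete or partial response.

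The same section then adds: "All other patients will be considered non-responders". It does not say whether this means other evaluable patients or other treated patients.

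The denominators are evaluable-only. Section 9.3.1 states: "Response rates will be calculated as the percent of RECIST response-evaluable patients who are responders". Section 9.3.3 divides both osteosarcoma counts by the number of response-evaluable patients. The 19 stage 1 patients in Section 9.2.2 and the accrual ranges in Section 9.1 are also expressed in evaluable patients.

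On replacement, Section 9.3.2 says: "Patients who are not evaluable for both disease control and response evaluation may be replaced for the purposes of the statistical rule". The 13+7 strata have no matching sentence; replacement there is only implied by the evaluable counts. Section 9.3.2 also counts as a disease control failure "any patient who dies because of treatment-related toxicity during the first six cycles of therapy", and says that an eligible patient who "receives one dose of XL184 and is lost to follow-up at (for example) the end of cycle 2 will not be considered" to have achieved disease control.

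Section 9.5 keeps every patient dosed per protocol in the toxicity evaluation. Section 9 has no efficacy analysis of all treated patients.

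**The concern.** A patient who takes the drug and leaves during Cycle 1 without progression or death on therapy meets none of the three routes. The first scheduled on-treatment tumor evaluation is at the end of Cycle 2 (Section 4.3.2), best response needs two determinations at least three weeks apart (Section 10.6), and disease control is judged at about four months. Such a patient is almost certain to be a failure on both endpoints.

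The exclusion is also related to the drug. Section 5.3.1 requires discontinuation for a list of serious toxicities, and Section 2.4.1 reports two of the kinds listed, hypertension and reversible posterior leukoencephalopathy syndrome, among the Cycle 1 dose-limiting events of the pediatric phase 1 trial. A patient removed for such an event would count for harm under 9.5 but not for efficacy under 9.4. Progression or death shortly after stopping in Cycle 1 is missed too, because the first route applies only while the patient is on therapy.

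The decision counts (3 responses in 20; 9 disease control successes or 5 responses in 29) would then be applied to a group selected for having tolerated the drug.

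**Working it through.** **Inputs.**
- 13+7 rule (Section 9.2.1): stop if 0 of 13; effective if at least 3 of 20; null 5%, alternative 25%.
- Osteosarcoma rule (Section 9.2.2): continue after 19 if at least 5 disease control successes or at least 2 responses; effective after 29 if at least 9 or at least 5. Null P(S) = 0.20 and P(R) = 0.05, with Pr(S|R) = 0.90.
- Excluded share d: the documents give no Cycle 1 drop-out rate, so d is varied. The largest value used comes from Section 9.1.2, where "a maximum of 36 patients are anticipated to get either 19 or 29 patients evaluable for response in the osteosarcoma stratum": (36 − 29)/36 = 7/36 = 19.4%.

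**Step 1: reproduce the plan's figures.** For the 13+7 rule at p = 0.05:
- exactly 1 of 13, then at least 2 of 7: 0.3512 × 0.0444 = 0.0156;
- exactly 2 of 13, then at least 1 of 7: 0.1109 × 0.3017 = 0.0335;
- at least 3 of 13: 0.0245.

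The sum is 0.0736 (stated 0.074). Power at 25% is 0.903, as stated.

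For osteosarcoma, each patient falls in one of four cells: response with control 0.9·P(R), response without control 0.1·P(R), control without response P(S) − 0.9·P(R), or neither. At the null these are 0.045, 0.005, 0.155 and 0.795. The exact two-stage calculation gives 0.108 (stated 0.11). The other three rows of the plan's table give 0.949, 0.904 and 0.789 (stated 0.95, 0.904, 0.79).

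**Step 2: effect of exclusion.** Assume that the null rates describe all treated patients and that every excluded patient is a failure. A rate p among treated patients becomes p/(1 − d) among evaluable patients. Pr(S|R) is unchanged, because no responder is removed. Running the same rules at the shifted rates gives these false-positive rates:

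| d | Response | Disease control | 13+7 rule | Osteosarcoma rule |
|---|---|---|---|---|
| 0 | 5.0% | 20.0% | 0.074 | 0.108 |
| 5% | 5.3% | 21.1% | 0.083 | 0.138 |
| 10% | 5.6% | 22.2% | 0.094 | 0.175 |
| 15% | 5.9% | 23.5% | 0.107 | 0.223 |
| 19.4% | 6.2% | 24.8% | 0.121 | 0.275 |

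**Step 3: effect on a reported rate.** Nine successes are 9/29 = 31.0% of evaluable patients. If all 36 had been treated, they would be 9/36 = 25.0%.

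**Step 4: the reverse case.** If the nulls and alternatives describe evaluable patients, counting early stoppers as failures multiplies every rate by (1 − d). At d = 10%, 13+7 power falls from 0.903 to 0.854 and osteosarcoma power at (0.42, 0.05) falls from 0.904 to 0.805. At 19.4% they are 0.790 and 0.666.

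**The case against.** The sentence making all other patients non-responders can be read as covering every treated patient. In that case Section 9.4 already does most of what is asked. That reading is possible, but it sits badly with the three-route definition and the evaluable-only denominators, so the text needs settling.

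The affected group is also narrow. Progression may be called on clinical or laboratory grounds without imaging (Section 4.3.2). For many toxicities the drug is held, and removal follows only after 21 days without recovery (Sections 5.2 and 5.3). A hold starting on Day 8 would therefore lead to removal at about Day 29, after Cycle 1. This limits the likely size of d but does not make it zero.

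Three stronger readings are tempting, and the documents do not support them:

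- *That 9.3.2 contradicts 9.4 on early drop-out.* The example in 9.3.2 is a patient lost at the end of Cycle 2, who is already evaluable under the one-cycle route and so is properly a failure. If the example is read broadly, 9.3.2 already counts early loss as a disease control failure. Neither reading shows a contradiction.
- *That all such patients will be dropped and replaced.* Replacement is permissive and is written only in the osteosarcoma section.
- *That about 19% of treated patients are expected to be excluded.* The 7 of 36 is an accrual ceiling with no stated cause. It may include ineligible or never-treated patients.

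The most serious objection concerns the benchmark. Section 1.1.2 compares osteosarcoma disease control with a historical cooperative-group experience, whose denominator is not given. If it used the same evaluability rule, the evaluable comparison is like with like, and changing the primary set would cost power, as Step 4 shows. This stands.

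**Conclusion.** The point holds in a conditional form. Taken literally, 9.4 leaves treated Cycle 1 stoppers without progression or death on therapy outside both denominators. Because they are almost always failures, this can only push the reported rates up, and no planned analysis would show by how much.

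Whether the false-positive rate also rises depends on the population behind the null rates. Section 9.2.2 words its nulls per individual patient, which leans towards treated patients but does not settle it. If they do describe treated patients, exclusion of 5% to 15% moves the 13+7 rule modestly (0.083 to 0.107 against 0.074) and the osteosarcoma rule more (0.14 to 0.22 against 0.11). The values at 19.4% (0.121 and 0.28) are an upper bound. If the benchmarks are evaluable-based, there is no inflation. A reader might infer that the stated error rates are simply wrong. They are not: they reproduce exactly for the evaluable population.

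**What to change.** Keep the evaluable-set rule as primary. In Sections 9.3.1, 9.3.3 and 9.4:

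1. Add a prespecified analysis of response (all strata) and disease control (osteosarcoma) in all eligible patients who received at least one dose, counting early stoppers as non-responders and not as disease control successes.
2. State whether each go/no-go decision holds in that set. Adding failures to the denominator does not change the number of successes, so the check must fix the sample size. One way is to apply each rule to the first 13 and 20, or 19 and 29, treated eligible patients in order of enrollment. If the nulls describe treated patients, this restores the stated 0.074 and 0.11.
3. Say which population the 5% and 20% null rates refer to.
4. Say whether the sentence on all other patients means other evaluable or other treated patients.

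The cost is some wording, one extra table and a slightly lower rate shown beside the primary one. No extra data are needed. Making all treated patients the primary decision set is optional, and should be weighed against the power loss that follows if the nulls turn out to be evaluable-based.
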